### • Follow up period

The patient will be asked to attend follow up visits every 4 weeks

### 1-to check the following:

- 1. The stability of the mini-implants
- 2. The activity of the appliance (force recalibration is required).
- 3. The amount of correction achieved.
- 4. Any inflammation related to the appliance or the miniimplants

2- Impressions will be taken (without the appliance in place) followed by digital scanning of produced models).

### **O** Criteria for discontinuing or modifying the allocated

In cases of prolonged swelling or pain related to the miniscrew, the patient will be given strict oral hygiene measures and may wait for three weeks before the beginning of retraction. -In cases of loose or broken mini-implant, the screw will be removed and replace the mini-implant after total resolution of the inflammation.

-In case of non-compliant patients.

### **o** Criteria of ending the distalization phase.

- Class I molar relation or at the end of pre-determined treatment duration (eight months).

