# **Outcome measure(s):**

	Outcome name	Measuring device	Measuring unit
Primary outcome	The total anteroposterior distance moved by the maxillary first molars.	Digital models using 3- shape scanner and program.	mm

		CBCT images using Anatomage software.	mm
Secondary outcomes	1-Maxillary first molar distalization rate.	Digital models using 3 shape scanner and program.	mm/month
	2-Maxillary first molar rotation	Digital models using 3 shape scanner and program.	Degree
	3- Intermolar width	Digital models using 3 shape scanner and program.	mm
	4-Maxillary first molar tipping and torque	CBCT images using Anatomage software.	Degree
	5-Maxillary first molar vertical changes	CBCT images using Anatomage software	mm

	6- Total anteroposterior distance moved by maxillary first and second premolars.	Digital models using 3 shape scanner and program.	mm
	7- Maxillary second molar tipping.	CBCT images using Anatomage software	Degree
	8-Maxillary third molar tipping	CBCT images using Anatomage software	Degree
	9-Maxillary third molar vertical changes	CBCT images using Anatomage software	mm
	10-Maxillary four incisors anteroposterior and vertical linear measurements.	CBCT images using Anatomage software	mm
	11- Maxillary four incisors torque.	CBCT images using Anatomage software	mm

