#### 2) Secondary outcomes:

The secondary outcomes were the changes in upper first molars rotation, intermolar width, tipping, torque, and vertical position, the upper first molars distalization rate, the changes in the anteroposterior position of the upper first and second premolars, tipping of upper second molars, tipping and vertical position of the upper third molars, and anteroposterior, vertical, and torque changes of the upper incisors.

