### 3) Methods of measuring of all outcomes:

Linear and angular measurements will be made on the pre, post and follow-up digital models and on the pre-and post distalization CBCT to assess the dental changes in intervention group.

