### **Participant timeline:**

1. The principal investigator will screen the potential patients through careful clinical examination of patients at the orthodontic department, Faculty of Oral and Dental Medicine, Future University in Egypt.

2. All recruited patients should fulfil the previously mentioned inclusion and exclusion criteria.

3. Every participant will be asked to sign an informed consent before the beginning of the study.

4. After patient's enrolment, each participant will be asked for preintervention records to ensure proper diagnosis.

[figure not shown]
5. The principal investigator will randomly allocate the patients to one of the intervention groups.

**6.** After patient's enrolment, pre-intervention records will be taken for each participant to ensure proper diagnosis (T0).

7. Every 4 weeks Each patient will have follow up visit, for appliance activation, uptake of impression for interim records and checking for mini-screws stability (T1-T7).

**8.** Post- records for each participant will be taken after duration of eight months (T8) at the same visit of appliance removal.

[figure not shown]
**9.** The principal investigator will continue the normal orthodontic treatment and achieved proper finished occlusion for every patient after the end of the study.

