### **C] Statistical Analysis:**

• The principal investigator will be responsible for the extraction of the required data from the CBCT taken before and after retraction as well as the study models taken at every follow up visit. The data will be sent to a specialized statistician.

• The specialized statistician will be responsible for the statistical analysis of the study by:

- 1. Presenting the data as mean, standard deviation (SD) and Standard error (SE) values.
- 2. Using Paired t-test to compare between the friction and the frictionless group of retraction as well as to compare between the pre-and post -treatment data for each group.

3. Using Anova test to determine the rate of anterior segment retraction.

4. Statistically evaluate the patient acceptance for both techniques.

• For this study, the specialized statistician will use IBM11 SPSS12 Statistics Version 20 for Windows to perform the required statistics.

• The significance level will be  $P \le 0.05$ . Highly significant variables are detected when P value is less than 0.01.

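### First-molar distalization rate, a listed secondary outcome, has no between-arm test in the analysis section and no defined time interval behind mm/month

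*Combined protocol and SAP*

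**What the plan says.** **Outcome.** The table under Outcome measure(s) lists "1-Maxillary first molar distalization rate", from digital models, in mm/month. The Secondary outcomes section repeats it as "the upper first molars distalization rate".

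**Analysis.** Section C] Statistical Analysis has one item on a rate, item 3: "Using Anova test to determine the rate of anterior segment retraction". Its one between-group test is item 2, a paired t-test "to compare between the friction and the frictionless group of retraction". Study design describes a two-arm parallel-group trial with 1:1 allocation, and the arms are third-molar extraction and non-extraction.

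**Time.** Criteria of ending the distalization phase gives the end as "Class I molar relation or at the end of pre-determined treatment duration (eight months)". Participant timeline item 7 says "Every 4 weeks Each patient will have follow up visit, for appliance activation, uptake of impression for interim records", covering T1 to T7. Item 8 says "Post- records for each participant will be taken after duration of eight months (T8) at the same visit of appliance removal". Data collection methods calls the models monthly. Methods of measuring of all outcomes refers to measurements "on the pre-and post distalization CBCT to assess the dental changes in intervention group".

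**The concern.** Serial models are planned at every visit, which is what a rate analysis needs, but the analysis section tests a different quantity in different groups. The test for first-molar rate could therefore be chosen after the data are seen.

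The choice of denominator could be made late in the same way, and it decides what the outcome means. A patient who reaches Class I early has a shorter active period than one who runs to eight months. Divided by active time, rate can show that one arm moved faster. Divided by eight months for everyone, it repeats the primary outcome in other units.

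The stopping rule also affects how the primary distance is read. If movement stops at Class I, distance is bounded by each patient's starting discrepancy, and the faster arm meets that bound more often. Without active time and early Class I reported by arm, a reader cannot judge how far this happened.

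**Working it through.** **1. Outcome against analysis.**

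| Needed for secondary outcome 1 | Written in Statistical Analysis |
|---|---|
| First molar | Anterior segment (item 3) |
| Distalization | Retraction (items 2 and 3) |
| Extraction v non-extraction | Friction v frictionless (item 2) |
| Independent arms | Paired t-test (item 2) |

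No item supplies a between-arm test of first-molar rate. In a parallel-group trial there is no pairing between arms for a paired test to use.

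**2. The plan's own figure.** Inputs from Sample size calculation: 3.17 (SD 0.81) mm and 4.32 (SD 0.79) mm, alpha 0.05 (two-sided assumed), power 80%.
- Pooled SD = sqrt((0.81² + 0.79²)/2) = 0.80; d = 1.15/0.80 = 1.437, as stated.
- Noncentral t power is 76.2% at 8 per group, 81.6% at 9 and 89.3% at 11. The stated 9 per group reproduces, for an independent-samples test on distance.

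**3. Fixed denominator.** Dividing every distance by 8 gives means of 3.17/8 = 0.396 and 4.32/8 = 0.540 mm/month, a difference of 0.144. The pooled SD becomes 0.80/8 = 0.100, so d is again 1.437. The t statistic and p-value are those of distance.

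**4. Active-time denominator.** For an assumed 4 mm:

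| Class I reached at month | Own-time rate (mm/month) | Rate over eight months |
|---|---|---|
| 4 | 4/4 = 1.00 | 0.50 |
| 5 | 4/5 = 0.80 | 0.50 |
| 6 | 4/6 = 0.67 | 0.50 |
| 8 | 4/8 = 0.50 | 0.50 |

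**5. Is early Class I plausible?** The literature review cites 0.70, 0.84 and 0.98 mm/month. Over eight months these give 5.6, 6.7 and 7.8 mm. At those rates the pilot means (3.17/4.32 mm) would be reached in 4.5/6.2, 3.8/5.1 and 3.2/4.4 months. Early finishing is plausible, but the documents do not show how often it occurs.

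**6. Month or four weeks.** Eight 4-week intervals are 32 weeks. A calendar month is 365.25/7/12 = 4.348 weeks, so 32 weeks is 7.4 months. The two units differ by 4.348/4 = 1.087, or 8.7%. This applies equally to both arms, so it changes the reported rate but not the test.

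**7. Effect on distance (assumption-based).** The documents give no distance to Class I in mm (eligibility sets a minimum discrepancy only), no pilot duration and no pilot stopping rule.
- *Case A: the pilot used the same stopping rule.* The 1.15 mm already includes it, and power is unchanged.
- *Case B: pilot distances were unbounded over eight months.* Model: eight-month movement Normal(3.17, 0.81) v Normal(4.32, 0.79), constant speed, distance needed for Class I uniform over a range, movement stopping at the first monthly visit where need is met or at month 8, independent t-test, 9 per group. No measurement error is added, because the pilot SDs are already observed values.

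| Assumed need (mm) | Early Class I, present v extracted | Power | Loss from 82% |
|---|---|---|---|
| 4-7 | 2% v 17% | 81% | under 1 point |
| 4-6 | 3% v 25% | 81% | under 1 point |
| 3.5-5.5 | 9% v 43% | 78% | about 4 points |
| 3-5 | 21% v 63% | 69% | about 12 points |

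The result depends on the assumed need and stopping model. With movement stopping exactly at Class I and need Normal with SD 1 mm, power is 42% at mean 4 mm, 73% at 5 mm and about 81% at 6 mm.

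**The case against.** **Item 2 could be read generously.** The group names and the talk of retraction look carried over from another study, so a statistician might apply item 2 to every outcome with an unpaired test. That intent is likely, but it is not what is written, and it would still leave the rate without a time interval. The objection does show that the problem is wider than item 3: the primary comparison depends on the same item 2, so both items need correcting together.

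**The stopping rule and the timeline might be read as contradictory.** They are not. The end criterion reads naturally as whichever comes first, and a patient could stop at Class I, be held, and be recorded at T8. What is missing is a sentence saying so. Early Class I would also be visible in the data, because correction is checked and impressions are taken at each visit. Only its handling and reporting are unspecified.

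**A reader might infer that the Class I stop leaves the trial underpowered.** The documents do not support that. Case A gives no loss, and Case B depends on a need they do not state. An assumed need of 2-4 mm would produce a large loss, but it fits the pilot poorly, since a mean of 4.32 mm would take extraction patients past Class I.

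**A reader might also infer that rate should replace distance.** It should not. Suppose the arms differ only in where movement stalls (assumed common speed 0.7 mm/month, SD 0.15, measurement SD 0.2 mm, need 3-5 mm, 9 per group). Active-period rate then has 54% power against 62% for distance.

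**Conclusion.** The point holds and should be fixed. Followed as written, the plan contains no extraction v non-extraction test of first-molar rate, and the interval behind mm/month is undefined. Neither statement rests on an assumption.

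The denominator is a matter of substance: a fixed eight months makes the rate test identical to the distance test, while active time can change an individual rate twofold in the 4 mm example. The record-timing gap for patients who reach Class I early is a clarification, not a contradiction.

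The loss of power on distance is conditional. It is nil if the pilot used the same stopping rule. If pilot distances were unbounded, it is about 0-4 points at 9 per group for a need of 3.5-5.5 mm or more and about 12 points at 3-5 mm, on the visit-stop model with uniform need. The sample size calculation is not in error on its own inputs.

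**What to change.** **(a) Statistical Analysis.** Replace item 3 with a between-arm comparison of first-molar rate. Take each patient's slope of first-molar position on time over the active distalization period from the planned serial models, average right and left molars to one value per patient, and compare arms by an independent-samples t-test with the difference and 95% CI. In item 2, name the extraction and non-extraction groups and replace the paired between-arm test with an independent-samples test. The paired test can stay for pre-post change within each group.

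**(b) Active period.** Define its start and end, how pauses count (for example while a mini-implant is replaced), and what is done in the analysis when one side reaches Class I first. Use one time unit, either the calendar month or four weeks.

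**(c) Timing and reporting.** Reconcile Criteria of ending the distalization phase with Participant timeline items 7 and 8 on record timing for patients who reach Class I before eight months. The clinical rule is for the investigators. Report active time and the share with early Class I by arm, so that distance can be read together with rate, and state the pilot's duration and stopping rule. Total distance stays primary, with rate as a supporting analysis.

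**Cost.** A short amendment and slightly more analysis. No extra visits, impressions or scans are needed, but start, stop and pause dates must be recorded for each patient.

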### **D]** Outcomes

### 1) Primary outcome

The primary outcome of the current study was to determine the total Anteroposterior position changes of upper first molars.

#### 2) Secondary outcomes:

The secondary outcomes were the changes in upper first molars rotation, intermolar width, tipping, torque, and vertical position, the upper first molars distalization rate, the changes in the anteroposterior position of the upper first and second premolars, tipping of upper second molars, tipping and vertical position of the upper third molars, and anteroposterior, vertical, and torque changes of the upper incisors.

### 3) Methods of measuring of all outcomes:

Linear and angular measurements will be made on the pre, post and follow-up digital models and on the pre-and post distalization CBCT to assess the dental changes in intervention group.

### **Participant timeline:**

1. The principal investigator will screen the potential patients through careful clinical examination of patients at the orthodontic department, Faculty of Oral and Dental Medicine, Future University in Egypt.

2. All recruited patients should fulfil the previously mentioned inclusion and exclusion criteria.

3. Every participant will be asked to sign an informed consent before the beginning of the study.

4. After patient's enrolment, each participant will be asked for preintervention records to ensure proper diagnosis.

[figure not shown]
5. The principal investigator will randomly allocate the patients to one of the intervention groups.

**6.** After patient's enrolment, pre-intervention records will be taken for each participant to ensure proper diagnosis (T0).

7. Every 4 weeks Each patient will have follow up visit, for appliance activation, uptake of impression for interim records and checking for mini-screws stability (T1-T7).

**8.** Post- records for each participant will be taken after duration of eight months (T8) at the same visit of appliance removal.

[figure not shown]
**9.** The principal investigator will continue the normal orthodontic treatment and achieved proper finished occlusion for every patient after the end of the study.

### **E]** Sample size calculation:

The sample size calculation is based on the findings of a pilot study, including three patients from each group, in which the upper first molar distalization amount was the primary outcome. The mean (standard deviation) values were 3.17(0.81) mm and 4.32 (0.79) mm in the TMP and TME groups, respectively. The effect size was 1. 437. With alpha level of 0.05 and a test power of 80%, the minimum estimated sample size was 18 patients (9 patients per group). Considering drop out a sample size of 11 per group is appropriate.

Sample size calculation is performed Using G\*Power version 3.1.9.2.

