Nur et al (2012), utilized the zygoma gear appliance to bilaterally distalize the maxillary molars and performed research to determine its dentoalveolar, skeletal, and soft tissue effects. The research group included fifteen patients (mean age, 15.87 1.09 years; range, 14–18 years), and lateral cephalometric images were obtained before and after distalization. A distalization force of 300 g per side was applied to the maxillary molars via the closed coil springs which replaced the heavy elastics in the previous design. The findings of the study showed that the maxillary molars were effectively distalized into a Class I relationship in all patients in a short time despite the presence of the maxillary second and third molars, the rate for the distal movement of the molars was 0.84 mm per month by total distalization of  $4.37 \pm 2.15$  mm without anchorage loss, while distal tipping measured only  $3.30^{\circ}$ ,maxillary first molars showed a slight intrusion (0.50 mm) and there were insignificant changes in both skeletal and soft tissue measurements.

Kilkis et al (2016), conducted a study to evaluate the dentoskeletal effects of the zygoma-gear appliance used for unilateral maxillary molar distalization, this study consisted of 21 patients with mean age  $15.68 \pm 2.18$  years and concluded that it was effective with significant amount of distalization for the maxillary first molar ( $5.31 \pm 2.46$  mm) in ( $0.45 \pm 0.12$  years), a 0.98 mm distalization rate per month

Aline Rode Santos et al (2017), conducted a tomographic study to evaluate the infra-zygomatic crest region thickness, in adult (male and female) patients. CBCT images from 40 patients were used to assess cross-sectional measurements of the infra-zygomatic crest region. Measurement 1 considered thickness 2 mm above the distobuccal root of the permanent maxillary first molar, while measurement 2 was taken 2 mm above the first measurement. The mean thickness of the infrazygomatic crest in males was 3.55 mm for measurement 1 and 2.84 mm for measurement 2, while in females these were 2.37 mm and 2.24 mm, respectively. The authors concluded that the overall mean thickness of the infrazygomatic crest was 2.49 mm with respect to measurement 1, and 2.29 mm for measurement 2, with no statistically significant differences between genders.

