# **B-Research question:**

Does extraction of the upper third molars have a different impact than nonextraction on distalizing maxillary first molars in Class II adolescents?

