### **Objectives of the study research**

### **Research hypothesis:**

The null hypothesis was that the presence and extraction of unerupted maxillary third molars would have a similar effect on the distalization amount of maxillary first molars and the other dental changes.

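### The 80% power is conditional on a difference and an SD estimated from six pilot patients; it should be stated as conditional, with a sensitivity range and a rule for reading a non-significant result

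*Combined protocol and SAP*

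**What the plan says.** Section E (Sample size calculation) bases the number of patients on "a pilot study, including three patients from each group". It prints the inputs: "The mean (standard deviation) values were 3.17(0.81) mm and 4.32 (0.79) mm in the TMP and TME groups, respectively". From an effect size of 1.437 it concludes "With alpha level of 0.05 and a test power of 80%, the minimum estimated sample size was 18 patients (9 patients per group", and it raises this to 11 per group for dropout without stating a dropout rate. It gives no confidence interval for either input, no sensitivity analysis and no clinically justified difference.

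The literature review (section III, Distalizers with skeletal anchorage) cites two zygoma-gear studies with first-molar distalization of 4.37 ± 2.15 mm (15 patients, bilateral; the sentence begins "the rate for the distal movement of the molars was 0.84 mm per month by total distalization of") and 5.31 ± 2.46 mm (21 patients, unilateral). The sample size section does not mention these SDs.

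The research hypothesis is a null under which presence and extraction of third molars "would have a similar effect on the distalization amount of maxillary first molars and the other dental changes".

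**The concern.** A power figure is only as firm as its inputs. Here both the difference and the SD are point estimates from six patients, and the SD rests on 4 degrees of freedom. The SDs that the protocol itself cites for a related appliance are about 2.7 to 3.1 times the pilot's (2.15/0.80 and 2.46/0.80), and the plan does not reconcile them.

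What is at stake is how a non-significant result will be read. A reader told that the trial had 80% power, and that the null is one of similar effect, could take P > 0.05 as evidence that extraction makes no difference. If the SD is materially above 0.80 mm, the trial could not exclude differences as large as its own 1.15 mm target.

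**Working it through.** **Inputs.** Means 3.17 and 4.32 mm, SDs 0.81 and 0.79 mm, 3 patients per group, alpha 0.05, 9 and 11 per group (sample size section); 1:1 parallel groups (Study design); SDs 2.15 and 2.46 mm (literature review, section III). Sidedness is not stated. The research question is non-directional, so two-sided is assumed.

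**1. The plan's own figure.**
- Difference = 4.32 − 3.17 = 1.15 mm.
- Pooled SD = √((0.81² + 0.79²)/2) = 0.800 mm.
- d = 1.15/0.800 = 1.437, as stated.
- Power is that of an independent two-sample t-test: noncentral t with 2n − 2 df and noncentrality d√(n/2). It is 76% at 8 per group, 82% at 9 and 89% at 11. The minimum of 9 reproduces. A one-sided t-test would give 7 per group and a paired test 6 pairs, so the plan's figure matches only the two-sided independent test.

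**2. What the pilot establishes (4 df).**
- Standard error = 0.800 × √(2/3) = 0.653 mm; t = 1.15/0.653 = 1.76, p = 0.15.
- 95% CI for the difference: 1.15 ± 2.776 × 0.653 = −0.66 to 2.96 mm.
- 95% CI for the SD: 0.800 × √(4/11.14) to 0.800 × √(4/0.484) = 0.48 to 2.30 mm.
- One-sided 80% upper limit for the SD: 0.800 × √(4/1.649) = 1.25 mm.
- 95% CI for d (noncentral t): −0.49 to 3.24. Over that range power runs from 5% to above 99%.

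**3. Power under other readings of the inputs.** The rows with a stated SD hold the difference at 1.15 mm.

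| Input | 9 per group | 11 per group |
|---|---|---|
| Pilot values, SD 0.80 mm | 82% | 89% |
| Small-sample-corrected effect, 1.437 × 0.798 = 1.147 | 63% | 73% |
| Mean over pilot uncertainty | about 64% | about 69% |
| Median over pilot uncertainty | about 76% | about 85% |
| SD 1.25 mm | 45% | 54% |
| SD 2.15 mm (cited) | 19% | 22% |
| SD 2.30 mm (pilot upper 95% limit) | 17% | 20% |
| SD 2.46 mm (cited) | 15% | 18% |

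The mean and median come from drawing the SD and the difference from the pilot's reference posterior and counting significance in either direction. Counting only the expected direction, the means are 63% and 67%.

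**4. Margin for error in the SD.** With 11 per group and no losses, 80% power needs d = 1.256. With a difference of 1.15 mm the SD may be at most 1.15/1.256 = 0.92 mm, about 14% above the pilot value.

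**5. Precision at 11 per group.** The expected 95% CI half-width is 2.086 × SD × √(2/11): 0.71 mm at SD 0.80, 1.11 mm at SD 1.25, and 1.9 to 2.2 mm at SD 2.15 to 2.46. At the last two SDs, the difference detectable with 80% power is 1.256 × SD = 2.7 to 3.1 mm.

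**The case against.** There is a fair case for leaving the section as it stands. The calculation is correct, and the plan does disclose its basis: it names the pilot, its size, both means, both SDs and the effect size before it states the power. What is missing is a sensitivity statement, not the source. The pilot's p = 0.15 adds little, since with 3 per group a true effect of 1.437 would reach significance only 27% of the time. All of this stands.

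A reader might infer from the cited SDs that the trial really has only 15–22% power. The documents do not support that.
- The figure merges two sample sizes and is the pessimistic end of a range that also extends above 99%.
- The SDs come from studies of a different, related appliance. One treated patients unilaterally, whereas this trial enrols bilateral cases. The other measured on lateral cephalograms, whereas this trial uses digital models and CBCT.
- Pairing those SDs with an unchanged 1.15 mm difference is an assumption.
- The pilot weighs against them. The value 2.46 mm lies outside its 95% interval. The value 2.15 mm lies inside, but a pooled SD of 0.80 mm or less would then have had probability of only about 3%.

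Nor do the documents say that P > 0.05 will be reported as similarity. The hypothesis is an ordinary null, so the misreading is a risk to be closed off, not a stated intention.

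The objection does not rescue 80% as an unconditional figure. The corrected effect and the average over the pilot's uncertainty both fall below 80% at 9 and at 11 per group, without any outside SD. Only the median at 11 per group, with no losses, lies above it.

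**Conclusion.** The point holds as one about conditional power, not about a miscalculation. The plan's 80% is right if the true difference is 1.15 mm and the true SD 0.80 mm, but six patients do not establish either value. Reasonable central figures are 63% to 76% at 9 per group and 69% to 85% at 11. The cited SDs give a pessimistic case of 15–19% and 18–22% respectively, provided the difference stays at 1.15 mm and those studies' variability carries over; the documents neither show this nor rule it out.

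These results assume a two-sided independent t-test and normally distributed outcomes with equal SDs. The values for 11 per group also assume no losses. The point affects what a non-significant result may be taken to mean. It does not invalidate the design.

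**What to change.** Keep 11 per group. In the sample size section, replace the unconditional statement with wording such as:

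> Nine per group gives 82% power (11 per group, 89%) only if the true difference is 1.15 mm and the SD 0.80 mm, as estimated from six pilot patients (SD 95% CI 0.48–2.30 mm). Power at 9 / 11 per group is 63% / 73% with the small-sample-corrected effect, 45% / 54% at SD 1.25 mm, and 15–19% / 18–22% at the SDs of 2.15–2.46 mm reported for a related appliance, assuming the same 1.15 mm difference.

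In the Statistical Analysis section, add:

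> The primary result is the between-arm difference in first-molar distalization with its 95% CI, from an independent two-sample comparison, the test on which the sample size is based. P > 0.05 will not be reported as showing a similar effect.

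The second insertion is also needed because that section currently names a paired t-test for the comparison between groups, which does not match the parallel-group design or the sample size calculation.

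The cost is wording only: no added patients, visits or procedures. The downside is that the stated power becomes less favourable.
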